**Table: Summary of protocol changes**

Date	Description of change
May 13, 2019	
Pre-enrollment refinement of randomization, allocation concealment, masking of outcome assessments, and inclusion/exclusion criteria
 

• Clarified that randomization occurs based on day of prescription drop off

• Added allocation concealment conducted by lead pharmacist using computer-generated random assignments prepared and communicated electronically by study statistician

• Changed masking for outcome assessors to be blinded to treatment group assignment

• Clarified enrollment criteria to include prescriptions written for individuals <18 years of age which were picked up by a designated family member <math>\geq 18</math> years of age

DISPOSE Protocol Supplement: Summary of Protocol Changes **PROTOCOL: Disposal Interventions for Safe Prescription Opioid Surplus Elimination (DISPOSE)**

**PRINCIPAL INVESTIGATOR: [name], PhD**

**ABSTRACT:**

Many people who receive a prescription for opioids report having leftover opioids once they are no longer needed to treat pain. These leftover opioids, which are rarely disposed of, can enable the opioid crisis by serving as a reservoir of drug available for misuse. For example, 90% of people who misuse prescription opioids report obtaining them from a family member or friend, or their own legitimate prescription. One way to reduce the amount of leftover opioids remaining in homes is to dispose of them once they are no longer needed. As a result, the Food and Drug Administration currently recommends that patients dispose of leftover prescription opioids by returning them to an authorized permanent collection site (e.g., medication drop boxes), or, when this is not feasible, flushing leftover opioid down the toilet. A newly available home disposal option involves use of a drug disposal kit. One such kit is DisposeRx. This product, which is available for purchase without a prescription, provides a safe and quick way to dispose of prescription medication. When a person mixes leftover drug with the DisposeRx powder and water, DisposeRx traps the medication in a gel which can then be safely disposed of in household trash. However, it is not known whether provision of drug disposal kits will increase the likelihood that leftover opioids will be disposed of by patients as compared to the currently accepted best practice, which is to provide instructions on how to safely dispose of leftover medications at home. This study will test the hypothesis that participants who receive a drug disposal kit such as DisposeRx will have the same rate of disposing of leftover prescription opioids as participants who are given standard instructions on how to dispose of leftover prescription opioids (i.e., currently accepted best practice). We will conduct a randomized controlled trial of individuals filling a new prescription for an opioid medication in the Johns Hopkins pharmacies to answer this question. Individuals will be called by telephone up to 6 weeks after they fill their prescription to determine whether or not they have disposed of their leftover prescription opioid medications, and if so by what means.

**OBJECTIVES:**

The primary objective of this study is to determine the impact of provision of the DisposeRx drug disposal kit on the proportion of participants who dispose of leftover prescription opioids once they are no longer required to treat pain. This aligns with the overall goal of reducing the presence of leftover opioids after participants conclude therapy, because leftover opioids serve as a reservoir for the misuse and diversion of opioids which can then contribute to the opioid crisis.

The secondary objective of the study is to determine the impact of Disposal Interventions (i.e., DisposeRx or an informational handout that lists disposal methods recommended by the Food and Drug Administration) on the proportion of participants who dispose of leftover prescription opioids in any manner.

## **BACKGROUND:**

The opioid crisis represents the most pressing public health epidemic at this time, with more than 47,000 deaths in 2017. While deaths from illicit fentanyl have recently increased, given that over 40% of all opioid overdose deaths involve a prescription opioid, nonmedical use of prescription opioids remains a key contributor to the crisis. Prescription opioids are the number one category of pharmaceutical products that Americans misuse, and 11.1 million Americans reported misusing opioids in 2017. Ninety percent of those who misuse prescription opioids report obtaining them from a family member or friend, or from their own legitimate prescription. Also, a majority of people who are prescribed opioids fail to adequately store or dispose of them once they conclude therapy. When people dispose of prescription opioids, they often do so using methods that are not recommended by the Food and Drug Administration. For example, only 9% of individuals prescribed opioids after surgery reported disposing of leftover medication in a manner recommended by the Food and Drug Administration. Thus, methods to enhance the safe disposal of leftover prescription opioids deserve investigation.

Different interventions are currently available to promote the safe disposal of leftover prescription opioids. One of the most basic methods is to provide patients with an educational pamphlet or written instructions describing recommended disposal methods. Past studies have examined the impact of these educational interventions and found either no change or an increase in the proportion of participants who dispose of leftover prescription opioids. For example, Rose and colleagues reported that the proportion of participants who disposed of leftover prescription opioids using a recommend method increased from 5% to 27% (difference 22%, 95% CI, 5% to 38%) when subjects were provided with an opioid disposal pamphlet.

An alternative disposal intervention involves providing patients with a drug disposal kit. These kits typically contain a substance that the patient mixes with leftover prescription opioids once they are no longer required to treat pain. One such kit is DisposeRx, a product that is now available at many major retailers without a prescription. The DisposeRx formulation is manufactured of components that are generally recognized as safe (GRAS) by the Food and Drug Administration; these substances are often included in various foods and drugs, and are not toxic. The desiccant silica powder is also listed by the FDA as a GRAS ingredient (GRAS Notice (GRN) No. 298:

<http://www.fda.gov/Food/FoodIngredientsPackaging/GenerallyRecognizedasSafeGRAS/GRASListings/default.htm>). Of note, while the kit can be purchased, Walmart currently offers

DisposeRx free of charge to patients at all of its pharmacy locations. To use DisposeRx, a participant combines the DisposeRx powder with water in the original prescription bottle and then shakes the mixture together. When activated by water, DisposeRx traps the drugs (i.e. pills, capsules, caplets, liquids or tablets) in a semi-solid gel. The trapped drug cannot be retrieved from the resulting gel material for abuse or leach into landfills. The participant can then throw away the biodegradable solid material in the prescription bottle as it is safe for the environment. Importantly, the contents of DisposeRx are also safe if eaten. To date, no published studies have examined the impact of any opioid disposal kits on rates of safe disposal of leftover prescription opioids. Disposal interventions are the focus of two trials on ClinicalTrials.gov, NCT03179566 and NCT03285061. However, both trials examine other drug disposal kits than DisposeRx.

At Johns Hopkins Outpatient Pharmacies, the current standard of care is that individuals who fill prescriptions are not provided with instructions on how to safely dispose of prescription opioids. Despite this case, opioid prescriptions have been a central focus of the Opioid Stewardship Clinical Community, since its inception in early 2017. Drawing on clinician leaders across the institution, the Opioid Stewardship Clinical Community has focused on improving the judicious use of prescription opioids from the time the medications are considered to their prescribing, dispensing, use, and finally disposal. JHHS and the Opioid Stewardship Clinical Community have undertaken a number of initiatives to enhance the ability of patients to dispose of prescription medications, including opioid prescriptions. For example, the Johns Hopkins Department of Pharmacy has installed drug disposal units for patients to drop off leftover prescription medications at outpatient pharmacies located at the Johns Hopkins Hospital and Johns Hopkins Bayview Medical Center in Baltimore. However, not all 11 Hopkins pharmacies support the drug disposal units. As a result, JHHS and Johns Hopkins Department of Pharmacy are considering alternate interventions to promote safe drug disposal. The goal of this randomized, controlled trial will help determine whether our health system should provide certain patients with individual drug disposal kits when an opioid prescription is filled at a Johns Hopkins pharmacy. This study is necessary because, as acknowledged above, no published studies have examined the impact of opioid disposal kits on rates of safe disposal of leftover prescription opioids.

Design: This study is a randomized controlled trial. This approach was selected to best achieve robust and unbiased results.

Setting: This study will take place in select Johns Hopkins Health System outpatient pharmacy locations.

Participant screening: As a part of routine care at Johns Hopkins pharmacies, a pharmacist currently examines and verifies every opioid prescription that is brought in to the pharmacy to be filled. The pharmacist who does this examination and verification is called the pre-verification pharmacist. This examination and verification is required by Johns Hopkins policy (available for review at Johns Hopkins Policy & Document Library at [https://hpo.johnshopkins.edu/hopkins/policies/65/14154/policy\\_14154.pdf?\\_=0.854965807447](https://hpo.johnshopkins.edu/hopkins/policies/65/14154/policy_14154.pdf?_=0.854965807447)). The pre-verification pharmacist currently examines various characteristics of the opioid prescription including, but not limited to the type of opioid (name, whether short-acting or longacting), dose, route, number of pills and days' supply. Characteristics of the individual for whom the prescription was written are also part of this state required examination and include demographics such as age and gender, the insurance company or payer, and the telephone number of the patient. The pre-verification pharmacist reviews this data using two computer systems, McKesson Enterprise Rx (an electronic management system specific to Johns Hopkins Pharmacy) and EPIC (the electronic health record for the Johns Hopkins Health System). All procedures performed by the pre-verification pharmacist that have been described up to this point take place as a part of routine care. This Johns Hopkins policy required review of the prescription and the patient which occurs during normal business hours in the Johns Hopkins Outpatient Pharmacies will serve as the review for eligible participants with qualifying prescriptions in this study.

Randomization and Disposal Intervention: Randomization will occur by day of the week using a computer generated schedule as determined by the study statistician. Randomization by day of the week was chosen due to pragmatic reasons, given logistical difficulties in the pharmacy of randomizing individual prescriptions. Randomization will occur to one of three possible conditions using an “add-on” design: (1) the ‘control’ group will receive standard of care, which is provision of no specific disposal information; (2) the ‘fact sheet’ group will receive an informational sheet with disposal instructions; or (3) the ‘drug disposal kit’ group will receive the same informational sheet with instructions, Dispose Rx, and instructions on how to use Dispose Rx. For example, on Monday all participants could receive an information sheet with Dispose Rx as the Disposal Intervention along with their opioid prescription. Then on Tuesday all participants could receive only an informational sheet with disposal instructions as the Disposal Intervention along with their opioid prescription. Then on Wednesday all participants could receive no intervention (current standard of care) when they pick up their opioid prescription. An IRB approved study team member will inform the pharmacist of the Disposal Intervention for that particular weekday. No change in any other aspect of the participant’s pharmacy encounter will take place (i.e., the participant will fill the opioid prescription for the amount/dose as originally prescribed).

Baseline data collection: Baseline information about the individual for whom the prescription was written will be collected from Enterprise Rx and EPIC using a standardized chart data extraction form (e.g., demographics [i.e., age, gender, race/ethnicity], opioid prescription characteristics, telephone number) by an IRB-approved member of the study team.

Follow up telephone survey: Participants will be contacted by an IRB-approved member of the study team via telephone at 3 weeks after filling the opioid prescription and asked to complete a standardized survey. Up to three contacts via telephone will be attempted between 20 and 26 days after the prescription is filled. If the participant has not completed opioid therapy at that time or does not respond to any of the 3 phone calls, they will be contacted at 6 weeks to complete the survey. For these participants, up to three contacts via telephone will be attempted between 40 and 46 days after the prescription fill.

During data collection and with annual progress reports to the IRB, we will include counts of the number of subjects who decline to provide data at the week 3 and week 6 outcome assessments, and provide counts of the number of subjects, if any, who express displeasure with learning that they have been entered in a research study without their prior consent.

We are requesting a waiver for consent for the randomization to the disposal intervention portion of this study; however, when we call patients at 3 and/or 6 weeks later, we will ask them if they are willing to answer survey questions related to the disposal of their opioid medication/s. If they do not want to respond to any questions, we will not continue with the survey nor will we attempt to contact them again. If the patients indicate they are willing to answer the survey questions, then we will obtain oral consent for the survey portion of this study from participants at that time.

Study duration: Each participant will be asked to complete one 6-minute telephone survey at 3 weeks after the date of filling the opioid prescription. Participants who have not stopped using

opioids at 3 weeks or who did not respond to any of the 3 phone calls at 3 weeks will be asked to complete a follow-up telephone survey at 6 weeks after the date of filling the original opioid prescription. No additional study visits or interactions will be required. This study is expected to begin as soon as IRB approval is obtained and will last for approximately one year to include data analysis.

**Blinding:** Participants and researchers will be aware (i.e., not be blinded) to the Disposal Intervention. It is not feasible to blind either group to either Disposal Intervention.

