## **Analysis Plan**

Sample size estimates: Sample size is calculated based on estimated effects on the primary outcome measure, the number of participants using a safe drug disposal method for leftover prescription opioids. This is defined as participants who report "yes" to disposing of leftover prescription opioid medication using a disposal intervention that aligns with recommendations from the Food and Drug Administration (i.e., using a take-back program, drug disposal kit, or flushing in the toilet) up to 6 weeks after prescription fill. At the time of writing this protocol, no published studies have examined the impact of disposal kits on rates of safe disposal of leftover prescription opioids. We estimate that the 'fact sheet' group will have a disposal rate of one in six patients (~17%), and that the 'drug disposal kit' group will have a disposal rate of one in three patients (~33%). To achieve 80% power with  $\alpha = 0.05$ , each group will require 126 patients. We will allocate patients 1:1:1 among the 'drug disposal kit' group, 'fact sheet' group, and 'control' groups, and thus require a sample size totaling 378 patients. Based on prior studies, we anticipate a dropout rate of 10-15%; allowing for a conservative non-response rate of 24.25%, we will need to enroll 499 participants.

We estimate that the 'no intervention' group (i.e., current standard of care) will have a disposal rate of 5%, based on previous studies of patients after surgery reporting disposal at 1 month. When we compare the 'no intervention' group with 'fact sheet' group, this sample will provide 82% power to detect a difference. When we compare the 'no intervention' group with the 'drug disposal kit' group, this sample will provide >99% power to detect a difference.

Primary analyses: We will use an intent-to-treat analysis approach, including all eligible patients in the group to which they were originally assigned. We will compare baseline characteristics and potential confounders between the three groups. Any imbalance will lead to additional analyses, as described in the "potential confounding" section below. The amount of opioids will be described as total morphine-equivalent mg using standard conversion tables from the CDC Guideline for Prescribing Opioids for Chronic Pain.

Aim 1: To compare disposal interventions on safe drug disposal up to 6 weeks after filling an opioid prescription.

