The primary outcome is the number of participants using a safe drug disposal method for leftover prescription opioids, as defined in the "sample size estimates." The primary comparison of interest is comparison of the 'drug disposal kit' group and the 'fact sheet' group. The secondary comparisons of interest are the comparisons of each of these two groups with the 'no intervention' group. Based on the study design and methods, we will examine outcomes for each individual at one point in time in follow up (i.e., 3 weeks or 6 weeks after filling at prescription). Thus, results from the 3-week follow up will be combined with results from the 6-week follow up for the purposes of statistical analyses. Additionally, the primary outcome of using a disposal intervention is only applicable for individuals who have completed their course of therapy. In other words, individuals who have not completed their course of opioid therapy would not be eligible to use a disposal intervention given they are still using their prescription opioid therapy. As a result, the primary outcome will be analyzed only in the subset of individuals who have reported that they have stopped taking prescription opioids at the time of follow up.

Preliminary analyses will use intent-to-treat analyses to compare the number of individuals reporting the use of a safe drug disposal method for leftover prescription opioids using chisquared tests to compare proportions. In an adjusted models for the primary analysis, we will use log-binomial regression to determine the risk ratio of safe drug disposal comparing two groups. We will conduct sensitivity analyses using Poisson models with robust error variance. We will present outcome measures with 95% confidence intervals and make no adjustment for multiple comparisons.

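### Whole days are randomised, but the sample size and the primary analysis treat participants as independent

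*Combined protocol and SAP*

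**What the plan says.** **Allocation.** The Randomization and Disposal Intervention paragraph of the protocol says: "Randomization will occur by day of the week using a computer generated schedule as determined by the study statistician". The reason is practical: "given logistical difficulties in the pharmacy of randomizing individual prescriptions". Its illustration gives one arm to everyone on a Monday, another on the Tuesday and the third on the Wednesday. The summary of protocol changes adds: "Clarified that randomization occurs based on day of prescription drop off".

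**Sample size.** The Analysis Plan assumes safe disposal in one in six with the fact sheet (about 17%) and one in three with the kit (about 33%), alpha 0.05 and 80% power. It concludes that "each group will require 126 patients", so 378 in total and 499 enrolled after 24.25% non-response. For the fact sheet against a control rate of 5%, "this sample will provide 82% power to detect a difference".

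**Analysis.** Aim 1 starts with chi-squared tests. For the adjusted primary analysis, "we will use log-binomial regression to determine the risk ratio of safe drug disposal comparing two groups". Then: "We will conduct sensitivity analyses using Poisson models with robust error variance". Further adjustment is planned only for covariates found to be imbalanced, with participant and prescription characteristics as the examples.

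**What is absent.** The plan gives no ICC, design effect, number of days, participants per day, random effect, GEE or clustered variance. On duration it says only that the study "will last for approximately one year to include data analysis".

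**The concern.** When whole days are allocated, the information about the arm contrast comes from days as well as from people. If two participants from the same day are more alike than two from different days, a method that counts them as independent understates the variance of the kit versus fact sheet comparison. The p-value is then too small, the 95% interval too narrow and the real power below the stated figure. This is the primary comparison, and the protocol's background says the trial is to inform whether the health system hands out kits.

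The protocol itself contains a possible source of such correlation. A study team member tells the pharmacist which arm applies that day, so a missed or wrong instruction would affect everyone on that day.

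A related gap is that the wording does not settle whether arms are drawn afresh for each calendar date or fixed to weekdays. With one arm per weekday there would be about five clusters for three arms, and arm would be confounded with weekday. No individual-level analysis could repair that.

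**Working it through.** **Step 1. Reproduce the plan's figures.** Inputs from the Analysis Plan: p1 = 0.17, p2 = 0.33, difference d = 0.16, mean 0.25, 80% power, alpha 0.05 (taken as two-sided).

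- Uncorrected n = [1.960 × √(2 × 0.25 × 0.75) + 0.842 × √(0.17 × 0.83 + 0.33 × 0.67)]² / 0.16² = (1.200 + 0.507)² / 0.0256 = 113.8.
- With continuity correction: (113.8 / 4) × [1 + √(1 + 4 / (113.8 × 0.16))]² = 125.98, i.e. the stated 126.
- The same corrected formula at 126 per group gives 81.6% for 5% against 17% (stated 82%).
- Enrolment: 378 / (1 − 0.2425) = 499.0 (stated 499).

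The stated figures are therefore those for independent individuals, inflated for non-response only. Without the continuity correction, 126 per group has 83.9% power for the primary comparison and 86.5% for fact sheet against control.

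**Step 2. Assumptions the documents do not supply.** ICC 0.01 to 0.05. Analysed participants per day (m), from 378 spread over 9, 6 or 3 months at 21 weekdays a month: 378/189 = 2, 378/126 = 3, 378/63 = 6. An extreme case of m = 10 means recruiting in about 38 weekdays.

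**Step 3. Effect of clustering.** Design effect DE = 1 + (m − 1) × ICC. Effective n per group = 126 / DE. Type I error of the unclustered test without continuity correction = 2 × [1 − Φ(1.96 / √DE)]. Intervals should be wider by a factor √DE.

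| m | ICC | DE | Type I error (uncorrected) | Power 17% v 33%, uncorrected / corrected | Power 5% v 17%, uncorrected / corrected | √DE |
|---|---|---|---|---|---|---|
| any | 0 | 1.00 | 5.0% | 83.9% / 80.0% | 86.5% / 81.6% | 1.000 |
| 2 | 0.01 | 1.01 | 5.1% | 83.5% / 79.6% | 86.2% / 81.1% | 1.005 |
| 3 | 0.05 | 1.10 | 6.2% | 80.3% / 75.7% | 83.2% / 77.2% | 1.049 |
| 6 | 0.05 | 1.25 | 8.0% | 75.0% / 69.5% | 78.1% / 70.8% | 1.118 |
| 10 | 0.05 | 1.45 | 10.4% | 68.6% / 62.0% | 71.9% / 63.0% | 1.204 |

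Without the correction, the stated 80% survives up to DE = 126 / 113.8 = 1.11, and the stated 82% up to 1.13.

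**Step 4. Simulation check.** Beta-binomial days, about 126 per arm, ICC 0.05.

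- Chi-squared test with a common rate of 25% (40,000 replicates), type I error uncorrected / corrected: 6.2% / 4.4% at m = 3; 7.7% / 6.0% at m = 6; 10.4% / 8.1% at m = 10.
- Log risk ratio (20,000 replicates), type I error with naive variance / day-clustered variance and a t reference: 5.7% / 4.5%; 7.2% / 4.6%; 9.9% / 4.4% for the same three values of m.
- Power of the day-clustered analysis for 17% against 33%: 77.6%, 71.7% and 64.6%.

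**The case against.** The strongest reply is that the harm may be slight. No document gives an ICC or a daily count, and a study of about a year suggests few participants per day. At 2 to 3 per day an uncorrected chi-squared test keeps at least 80.3% primary power. A corrected test keeps type I error below 5% (4.4% at m = 3, ICC 0.05). One test does not suffer both harms. This stands, and it is why the effect is given as a range.

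There is also incidental slack. Taken literally, one in six against one in three needs 117 per group with the correction, so 126 would cover a design effect of about 1.08. If dropout is the anticipated 10% to 15% rather than 24.25%, 499 enrolled yields 424 to 449 respondents, or 141 to 150 per group, enough for a design effect of 1.12 to 1.19 with the correction. But the stated 126 comes from the rounded rates, and restricting the primary outcome to those who have stopped opioids would use some of the dropout margin. Spare numbers help power; they do not correct the standard error or the type I error.

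The Poisson model with robust variance is not an answer as written. It is only a sensitivity analysis, and it is not said to be clustered on day.

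A delivery lapse changes no outcome if neither intervention works, so it creates no correlation under that null. The null for the primary comparison, however, is kit equal to fact sheet. If both beat control, lapses do produce days that differ. A lapse at one pharmacy would affect only that pharmacy's day, so the effective cluster may be smaller than the m used here; that part stands.

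Finally, the weekday illustration is only an example, and a computer-generated schedule fits date-level assignment at least as well. The fixed-weekday reading is a possibility to exclude, not an established flaw.

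**Conclusion.** The concern holds. The analysis does not match the randomisation, and the stated sample size contains no planned allowance for clustering. The size of the consequence is unknown. It is nil at ICC zero and small at 2 to 3 analysed participants per day. It is material at 6 per day with ICC 0.05, and serious in the extreme case of 10 per day, where type I error is about 10% and primary power 69% uncorrected or 62% corrected. These figures rest on the assumed ICC and recruitment pace, and on date-level allocation with many days. A schedule fixed by weekday would be worse than a simple design effect shows. The plan needs correcting whatever the ICC proves to be, because the present methods cannot show whether it matters.

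**What to change.** 1. **Analysis.** Fit the primary log-binomial (or Poisson) model with the randomised day as the cluster: drop-off date, or pharmacy-day if schedules differ by pharmacy. Use GEE or cluster-robust variance with a small-sample correction. Replace the plain chi-squared test with a cluster-adjusted one, and state that the Poisson robust variance is clustered on the same unit.
2. **Power.** Replace the single 80% and 82% with power at 126 per group over a stated range of ICC and participants per day. Say whether the chi-squared calculation is continuity corrected.
3. **Schedule.** State whether calendar dates or fixed weekdays were randomised and whether pharmacies share a schedule. If dates are already assigned, describe the schedule as used. If not, randomise dates; balancing arms within weekday is a sensible option but not essential to this point.
4. **Data.** Record drop-off date and pharmacy for each participant. Neither is among the protocol's examples of extracted items. That list is not exhaustive, and the fill date must already be held to time the calls, but it may differ from the drop-off date.

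**Cost.** Revised wording and two data fields. Under the assumptions above, intervals widen by 0.5% to 12% at 2 to 6 per day. No extra patients are needed if the lower power is accepted and stated. Keeping 80% on the plan's own continuity-corrected basis would need 507 enrolled at DE 1.01 (3 × 128 / 0.7575), 626 at DE 1.25 (3 × 158 / 0.7575) and 725 at DE 1.45 (3 × 183 / 0.7575), instead of 499.

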### **INCLUSION/EXCLUSION CRITERIA:**

#### Inclusion Criteria

1. Adult participants (age  $\geq 18$  years) who pick up an opioid prescription for themselves or a family member at a Johns Hopkins pharmacy
2. English speaking
3. Residential address and phone number in the United States
4. Filling a new prescription consisting of an immediate release opioid medication (i.e., immediate release morphine, oxycodone, hydromorphone, hydrocodone, tramadol; alone or in combination with acetaminophen) with  $\leq 7$  days' supply

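### Nothing in the plan keeps whoever judges eligibility unaware of the day's arm or checks entered against qualifying prescriptions, so entry could differ by arm

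*Combined protocol and SAP*

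**What the plan says.** Under Participant screening, the pre-verification pharmacist reviews every opioid prescription brought in, using Enterprise Rx and EPIC. That routine review "will serve as the review for eligible participants with qualifying prescriptions in this study".

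Under Randomization and Disposal Intervention, the unit is the day: "Randomization will occur by day of the week using a computer generated schedule as determined by the study statistician". Then "An IRB approved study team member will inform the pharmacist of the Disposal Intervention for that particular weekday". The text does not say which pharmacist is told, or at what time.

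The summary of protocol changes lists a pre-enrollment refinement: "Added allocation concealment conducted by lead pharmacist using computer-generated random assignments prepared and communicated electronically by study statistician". The same entry ties randomization to the day of prescription drop off and masks the outcome assessors. The Blinding paragraph says "Participants and researchers will be aware (i.e., not be blinded) to the Disposal Intervention".

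For entry, "We are requesting a waiver for consent for the randomization to the disposal intervention portion of this study". The criteria are mainly age, US address and phone number, opioid type, days' supply and prior opioid on the medication list. They also include "English speaking" and, in Inclusion 1, who picks up the prescription.

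The Analysis Plan describes an intent-to-treat approach, "including all eligible patients in the group to which they were originally assigned". It adds a baseline comparison, with covariate adjustment if measured variables are imbalanced.

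**The concern.** Random allocation of days makes the arms comparable only if the people counted on each day are chosen in the same way whatever the arm. Once the day's arm has been announced, it is not concealed for anyone screened later that day. If the same staff decide who qualifies, knowledge of the arm can affect who enters, without any intent.

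There are two plausible routes. First, language is not among the characteristics that Participant screening lists for the routine review, so it may rest on an impression. Second, kit and fact-sheet days require someone to recognise a qualifying person and hand something over, whereas control days do not. A busy counter could therefore miss people on hand-out days.

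The planned analysis would neither show nor repair this. A person never flagged is not in the analysed group. Adjustment reaches only measured variables, and neither the baseline list nor the named confounders mention language or inclination to dispose. The counts promised under Follow up telephone survey are of people who decline the survey or object to having been enrolled, not of qualifying or eligible people by arm. At stake is a modest spurious or inflated difference in safe disposal between arms.

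**Working it through.** **1. The plan's own figure.** The Analysis Plan gives about 17% (one in six) for the fact sheet, about 33% (one in three) for the kit, α = 0.05, 80% power and 126 per group. Taking p₁ = 0.17, p₂ = 0.33, p̄ = 0.25 and a two-sided test (sidedness is not stated):

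n₀ = [1.960·√(2·0.25·0.75) + 0.842·√(0.17·0.83 + 0.33·0.67)]² / 0.16² ≈ 113.8, that is, 114.

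With the continuity correction, n = (n₀/4)·[1 + √(1 + 4/(n₀·0.16))]² ≈ 126. This matches. Enrollment: 378/(1 − 0.2425) = 499.0, also as stated. The planning rates are therefore a fair base for an illustration. The planned difference is 16 points with the rounded rates and 16.7 points with the exact fractions.

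**2. Selective omission, near worst case.** Suppose a fraction m of those who would not dispose is missed and no disposer is missed. The documents give no value for m; 10% and 20% are assumptions. For a true rate p:

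observed rate = p / [p + (1 − p)(1 − m)]

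| m | Kit, p = 1/3 | Shift | Fact sheet, p = 1/6 | Shift | Net shift, kit minus fact sheet |
|---|---|---|---|---|---|
| 0.10 | 0.3333/(0.3333 + 0.6000) = 35.7% | +2.4 | 0.1667/(0.1667 + 0.7500) = 18.2% | +1.5 | +0.9 |
| 0.20 | 0.3333/(0.3333 + 0.5333) = 38.5% | +5.1 | 0.1667/(0.1667 + 0.6667) = 20.0% | +3.3 | +1.8 |

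If omission occurs on kit days only, the bias in the primary comparison is the kit shift, 2.4 to 5.1 points. If it is equal on fact-sheet days, which also need a hand-out, the bias is the last column, 0.9 to 1.8 points.

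**3. Imperfect prediction, no true effect.** Staff cannot foresee disposal weeks ahead, so a softer model is more realistic. Assume that both arms truly have a rate of 1/6, that half the people have a low and half a high propensity to dispose, and that a fraction f of the low-propensity half is missed on kit days only:

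kit rate = [0.5(1 − f)·low + 0.5·high] / [0.5(1 − f) + 0.5]

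- Rates 10% and 23.3%: f = 10% gives 17.0% (+0.4 points); f = 50% gives 18.9% (+2.2 points). With 126 per group, the two-sided rejection rate rises from 5% to between 5.1% and 7.5%.
- Rates 5% and 28.3%: f = 10% gives 17.3% (+0.6 points); f = 50% gives 20.6% (+3.9 points). The rejection rate is 5.2% to 12.4%.

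These rejection rates treat people as independent and leave out any correlation within days.

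**4. Does any text close the gap?** The concealment entry may hide future days' assignments, but it does not say that the screening pharmacist is unaware of the current day's arm. The masking it adds is for outcome assessors. No paragraph requires eligibility to be settled before the arm is known, or compares entered with qualifying prescriptions.

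**The case against.** The strongest reply is that the link is inferred. Screening is done by a pre-verification pharmacist, concealment is held by a lead pharmacist, and the person told the arm is only called the pharmacist. They may be different people. This stands: arm-aware review is the natural reading, not a stated fact.

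Second, discretion is narrow. The review is required for every opioid prescription, most criteria can be read from records, and collecting for a family member is expressly allowed. With a consent waiver there is no arm-aware consent discussion at entry, which is a common route for selection. This also stands. It limits the problem to language and to failures of flagging.

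Third, the analysis already covers all eligible patients. Read literally, that would answer the point, but the plan does not say how the eligible set is built. If it consists of those flagged at the pharmacy, the missing people are not in it.

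A reader might infer that control participants are found from records while kit participants are found at the counter. The documents do not say so. Baseline extraction is described once, with no difference by arm. A reader might also take the 5-point shift as the expected bias. It is not: it assumes that only non-disposers are missed, and on kit days only.

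**Conclusion.** The plan does not show that entry is independent of the day's arm. That is a real gap, worth closing before the results are relied on. Its size is unknown. The near worst case is 2.4 to 5.1 points for 10% to 20% omission of non-disposers on kit days alone. It falls to 0.9 to 1.8 points if fact-sheet days are affected equally, and is 0.4 to 3.9 points under the softer models with 10% to 50% omission. All of these are well below the planned difference, so selection of this kind could distort the estimate but would have to be very strong to produce the planned effect alone.

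A reader might go further and conclude that randomizing by day no longer protects the comparison. The documents do not support that. Record-based criteria, the consent waiver and the intention to analyse all eligible patients as assigned all limit the scope for selection. The conclusion rests on reading the screening and randomization paragraphs as involving the same pharmacy staff, with the arm announced before review.

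**What to change.** Define the enrolled set from records, by one rule in all arms:

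- State who receives the day's assignment and when.
- For each study day, a team member masked to the schedule lists all prescriptions that meet Inclusion 4 from Enterprise Rx, applies the remaining record-based criteria using data dated before the fill, and locks the list before calls begin.
- Confirm criteria that are not in the records (language, who picked up) at the follow-up call. The caller is masked and asks the same questions in every arm.
- Analyse everyone on the list by the arm of the drop-off day, whether or not an item was handed out. Using the drop-off day avoids misclassification when drop-off and fill fall on different days.
- Report qualifying, eligible and entered counts by arm.

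The cost is a little more record work in systems that the team already extracts, and slight dilution of the kit and fact-sheet effects by people who did not receive the item. Criteria confirmed by phone stay unknown for non-responders, so their number should also be shown by arm. If the team already builds its list this way, the change is a few sentences.
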